13.2.2. Severity Assessment

Severity Assessment – A qualitative assessment of the degree of intensity of an adverse event as determined by the Investigator or reported to him/her by the subject. The assessment of severity is made irrespective of test article, study treatment or study procedure relationship or seriousness of the event and should be evaluated according to the following scale:

- Mild – Event is noticeable to the subject but is easily tolerated and does not interfere with the subject's daily activities.
- Moderate – Event is bothersome, possible requiring additional therapy, and may interfere with the subject's daily activities.
- Severe – Event is intolerable, necessitates additional therapy or alteration of therapy and interferes with the subject's daily activities.

Clinical Study Protocol

Johnson & Johnson Vision Care, Inc.

13.3. Documentation and Follow-Up of Adverse Events

The recording and documenting of adverse events (ocular and non-ocular) begin when the subjects are exposed to the test article, study treatment or study procedure. Adverse events reported before the use of test article, start of study treatment, or study procedures will be recorded as medical history. However, if the condition deteriorates at any time during the study it will be recorded and reported as an AE. Untoward medical events reported after the subject's exit from the study will be recorded as adverse events at the discretion of the Investigator.

Upon finding an adverse event, the Principal Investigator will document the condition in the subject record and in the eCRFs and complete the Adverse Event eCRF.

Complete descriptions of all adverse events must be available in the subject record. All Adverse Events including local and systemic reactions not meeting the criteria for "serious adverse events" shall be captured on the appropriate case report form or electronic data system. All adverse events occurring while the subject is enrolled in the study must be documented appropriately regardless of relationship.

It is the Investigator's responsibility to maintain documentation of each reported adverse event. All adverse events will be followed in accordance with applicable licensing requirements. Such documentation will include the following:

- Adverse event (diagnosis not symptom).
- Drawings or photographs (where appropriate) that detail the finding (e.g., size, location, and depth, etc.).
- Date the clinical site was notified.
- Date and time of onset.
- Date and time of resolution.
- Adverse event classification, severity, and relationship to test articles, as applicable.
- Treatment regimen instituted (where appropriate), including concomitant medications prescribed, in accordance with applicable licensing requirements.
- Any referral to another health care provider if needed.
- Outcome, ocular damage (if any).
- Likely etiology.
- Best corrected visual acuity at the discovery of the event and upon conclusion of the event, if the AE is related to the visual system.

Upon discovery of an AE that is deemed 'possibly related' or 'related' to the test article or study procedures (whether related to the visual system or not), an AE review form [REDACTED] must be completed. Additional dated and initialed entries should be made at follow-up evaluations. Separate forms must be completed for each eye if the AE is bilateral.

In addition, if an infiltrate(s) is present, he/she will complete the Corneal Infiltrate Assessment eCRF. Where necessary, a culture of the corneal lesion will be collected to determine if the

Clinical Study Protocol

Johnson & Johnson Vision Care, Inc.

infection is microbial in nature. If cultures are collected, the date of culture collection and laboratory utilized will be recorded.

Changes in the severity of an AE shall be documented to allow an assessment of the duration of the event at each level of intensity to be performed. Adverse events characterized as intermittent require documentation of the onset and duration of each episode. Changes in the assessment of relationship to the Test Article shall also be clearly documented.

Subjects who present with an adverse event shall be followed by the Investigator, within licensure, until all signs and symptoms have returned to pre-treatment status, stabilized, or been satisfactorily resolved. If further treatment beyond licensure is required, the patient will be referred to the appropriate health care provider. The Investigator will use his/her clinical judgment as to whether a subject reporting with an adverse event will continue in the study. If a subject is discontinued from the study, it will be the responsibility of the Investigator to record the reason for discontinuation. The Investigator will also document the adverse event appropriately and complete the Adverse Event eCRF. Any subjects with ongoing adverse events related to the test article, study treatment or study procedures, as of the final study visit date, should be followed to resolution of the adverse event or until referral to an appropriate health care provider, as recommended by the Investigator. Non-ocular adverse events that are not related to the test article, study treatment, or study procedures may be recorded as “ongoing” without further follow-up.

13.4. Reporting Adverse Events

The Investigator will notify the Sponsor of an adverse event by e-mail, facsimile, or telephone as soon as possible and no later than 24 hours from discovery for any serious /significant adverse events, and 2 days from discovery for any non-significant adverse event. In addition, a written report will be submitted by the Principal Investigator to the IEC/IRB according to their requirements (section 13.4.2). The report will comment whether the adverse event was considered to be related to the test article, study treatment or study procedures.

13.4.1. Reporting Adverse Events to Sponsor

Serious/Significant Adverse Events

The Investigator will inform the sponsor of all serious/significant adverse events occurring during the study period as soon as possible by e-mail or telephone, but no later than 24 hours following discovery of the event. The Investigator is obligated to pursue and obtain information requested by the Sponsor in addition to that information reported on the eCRF. All subjects experiencing a serious/significant adverse event must be followed up and all outcomes must be reported.

When medically necessary, the Investigator may break the randomization code to determine the identity of the treatment that the subject received. The Sponsor and study monitor should be notified prior to unmasking the test articles.

In the event of a serious/significant adverse event, the Investigator must:

Clinical Study Protocol

Johnson & Johnson Vision Care, Inc.

- Notify the Sponsor immediately.
- Obtain and maintain in the subject's records all pertinent medical information and medical judgment for colleagues who assisted in the treatment and follow-up of the subject.
- Provide the Sponsor with a complete case history which includes a statement as to whether the event was or was not related to the use of the test article.
- Notify the IEC/IRB as required by the IEC/IRB reporting procedure according to national regulations.

Unanticipated (Serious) Adverse Device Effect (UADE)

In the event of an Unanticipated (Serious) Adverse Device Effect (UADE), the Investigator will submit a report of the UADE to the Sponsor and IEC/IRB as soon as possible, but no later than 24 hours after the Investigator first learns of the effect. This report is in addition to the immediate notification mentioned above.

The Sponsor must conduct an evaluation of the UADE and must report the results of the evaluation to FDA, the IEC/IRB and participating Investigators within 10 working days after the Sponsor first receives notification of the effect.

Non-Serious Adverse Events

All non-serious adverse events, including non-serious adverse device effects, will be reported to the sponsor by the Investigator no later than 2 days from discovery.

13.4.2. Reporting Adverse Events to the Responsible IEC/IRB and Health Authorities

Adverse events that meet the IEC/IRB requirements for reporting must be reported within the IEC/IRB's written guidelines. Each clinical site will refer to and follow any guidelines set forth by their Approving IEC/IRB. Each clinical site will refer to and follow any guidelines set forth by their local governing Health Authorities.

The Sponsor will report applicable Adverse Events to the local health authorities according to the written guidelines, including reporting timelines.

13.5. Event of Special Interest

None.

13.6. Reporting of Pregnancy

Subjects reporting pregnancy (by self-report) during the study will be discontinued after the event is recorded as an Adverse Event. Once discontinued, pregnant participants and their fetuses will not be monitored for study related purposes. Pregnant participants are not discontinued from contact lens or solution related studies for safety concerns, but due to general concerns relating to pregnancy and contact lens use. Specifically, pregnant women are discontinued due to fluctuations in refractive error and/or visual acuity that occur secondary to systemic hormonal changes, and not due to unforeseen health risks to the mother or fetus.

Clinical Study Protocol

Johnson & Johnson Vision Care, Inc.

14. STATISTICAL METHODS

14.1. General Considerations

Statistical Analysis will be undertaken by the sponsor or under the authority of the sponsor. A general description of the statistical methods to be implemented in this clinical trial is outlined below. More details will be included in the stand-alone Statistical Analysis Plan (SAP). The SAP will be developed and finalized prior to database lock.

All data summaries and statistical analyses will be performed using the SAS software Version 9.4 or higher (SAS Institute, Cary, NC).⁵ Throughout the analysis of data, the results for each subject/eye will be used when available for summarization and statistical analysis. Unscheduled visits will be summarized separately and will be excluded from the efficacy analysis.

Summary tables (descriptive statistics and/or frequency tables) will be provided for all baseline variables, efficacy variables and safety variables as appropriate. Continuous variables will be summarized with descriptive statistics (n, mean, standard deviation (SD), median, minimum and maximum). Frequency count and percentage of subjects or eyes within each category will be provided for categorical data.

14.2. Sample Size Justification

This study is designed and powered to demonstrate superiority of the Test lens compared to the Control lens with respect to the primary and secondary endpoints. Sample size was calculated to achieve a statistical power of 90% for each primary and secondary endpoint.

Sample size calculation was based on historical data from 4 hard locked studies (████████████████, ██████████, ██████████, and ██████████) and the interim read data from a single-arm study ██████████. ██████████, ██████████, and ██████████ used a 2×2 crossover design and ██████████ is a two-arm parallel study. The Test lens in these studies are the same as the Test lens in the current study. The 2-week follow-up evaluation data for the Test lens in the first study period from the three crossover studies and ██████████, and the interim data from ██████████ for the Control lens (DT1) were used in the sample size estimation. Table 9 below presents the descriptive statistics for the primary and secondary endpoints from these studies.⁶⁻⁹

Table 9: Descriptive Summary for the Primary and Secondary Endpoints at 2-week Follow-up from Historical and Interim Data

Study	Endpoint	Response	Test Lens (TRP-200)	Control Lens (DT1)
Test lens: ████████████████	End of day comfort (Primary): “Comfort at the End of the Day”	Very Satisfied	108 (47.6%)	16 (22.2%)
		Satisfied	80 (35.2%)	19 (26.4%)
		Neither Satisfied nor Dissatisfied	19 (8.4%)	9 (12.5%)

Clinical Study Protocol
Johnson & Johnson Vision Care, Inc.

Study	Endpoint	Response	Test Lens (TRP-200)	Control Lens (DT1)
Control Lens: [REDACTED]		Dissatisfied	13 (5.7%)	20 (27.8%)
		Very Dissatisfied	7 (3.1%)	8 (11.1%)
Test lens: [REDACTED]	Digital Device Use (Secondary 1): “Reduction in the feeling of tired eyes from using a computer or other digital device”	Not Applicable	11 (4.8%)	2 (2.8%)
		Excellent	86 (37.9%)	14 (19.4%)
		Very Good	66 (29.1%)	15 (20.8%)
		Good	43 (18.9%)	28 (38.9%)
		Fair	10 (4.4%)	9 (12.5%)
		Poor	11 (4.8%)	4 (5.6%)
Test lens: [REDACTED]	Comfort throughout the day (Secondary 2): “I could wear these contact lenses comfortably for as long as I wanted to”	Strongly Disagree	10 (2.7%)	11 (15.3%)
		Disagree	44 (11.9%)	22 (30.6%)
		Neither Agree Nor Disagree	33 (8.9%)	8 (11.1%)
		Agree	155 (41.8%)	15 (20.8%)
		Strongly Agree	129 (34.8%)	16 (22.2%)
Test lens: [REDACTED]	Comfortable vision while night driving (Secondary 3): “Ability to see comfortably while driving at night”	Not Applicable	8 (2.2%)	2 (2.8%)
		Excellent	184 (49.6%)	19 (26.4%)
		Very Good	99 (26.7%)	18 (25%)
		Good	60 (16.2%)	19 (26.4%)
		Fair	13 (3.5%)	9 (12.5%)
		Poor	7 (1.9%)	5 (6.9%)

For sample size estimation, a 20% difference in subjects endorsing the best two response options (Top 2 box, T2B) was assumed between the Test and Control lens groups, to obtain a relatively conservative sample size for a statistical power of 90% for the primary endpoint and for each secondary endpoint. The type I error rate used in the sample size calculation was based on the significance level specified in Section 14.4 (i.e., 2-sided alpha of 0.05 for the primary endpoint test, 0.025 for each of the first two secondary endpoints tests, and 0.0125 for the last secondary endpoint test). Sample size was estimated using the PROC POWER procedure in the SAS software Version 9.4 based on the Pearson chi-square test for two proportions.

End of day comfort

End of Day Comfort will be measured using a single item “Comfort at the End of the Day” at 2-week follow-up with a 5-point Likert scale (1: Very Satisfied, 2: Satisfied, 3: Neither Satisfied nor Dissatisfied, 4: Dissatisfied and 5: Very Dissatisfied). Responses will be

Clinical Study Protocol

Johnson & Johnson Vision Care, Inc.

converted into a binary variable for the purpose of analysis (Very Satisfied or Satisfied = 1 and others = 0). Assuming a 20% difference in T2B between the study lenses (Test = 68% and Control = 48%), sample size was calculated to achieve 90% power for demonstrating statistical superiority at a 2-sided type I error of 0.05.

Digital device use

Digital device use will be measured using a single item “Reduction in the feeling of tired eyes from using a computer or other digital device” at 2-week follow-up with a 5-point Likert scale (1: Excellent, 2: Very Good, 3: Good, 4: Fair and 5: Poor) with a “Not Applicable” response option. Responses will be converted into a binary variable for the purpose of analysis (Excellent or Very Good = 1 and others = 0) and “Not Applicable” will not be included in the analysis. Assuming a 20% difference in T2B between the study lenses (Test = 61% and Control = 41%), sample size was calculated to achieve 90% power for demonstrating statistical superiority at a 2-sided type I error of 0.025.

Comfort throughout the day

Comfort throughout the day will be measured using a single item “I could wear these contact lenses comfortably for as long as I wanted to” at 2-week follow-up with a 5-point Likert scale (1: Strongly Disagree, 2: Disagree, 3: Neither Agree Nor Disagree, 4: Agree and 5: Strongly Agree). Responses will be converted into a binary variable for the purpose of analysis (Strongly Agree or Agree = 1 and others = 0). Assuming a 20% difference in T2B between the study lenses (Test = 63% and Control = 43%), sample size was calculated to achieve 90% power for demonstrating statistical superiority at a 2-sided type I error of 0.025.

Comfortable vision while night driving

Comfortable vision while night driving will be measured using a single item “Ability to see comfortably while driving at night” at 2-week follow-up with a 5-point Likert scale (1: Excellent, 2: Very Good, 3: Good, 4: Fair and 5: Poor) with a “Not Applicable” response option. Responses will be converted into a binary variable for the purpose of analysis (Excellent or Very Good = 1 and others = 0) and “Not Applicable” will not be included in the analysis. Assuming a 20% difference in T2B between the study lenses (Test = 73% and Control = 53%), sample size was calculated to achieve 90% power for demonstrating statistical superiority at a 2-sided type I error of 0.0125.

Table 10 below summarizes the required number of completed subjects to achieve 90% statistical power for the primary and secondary endpoints.

Table 10: Sample Size Estimation for the Primary and Secondary Endpoints

Endpoint Type	Endpoint	Two-sided Type I Error	Sample Size (N/arm)	Power
Primary	End of day comfort	0.05	126	90%
			95	80.2%
Secondary	Digital device use	0.025	153	90%

Clinical Study Protocol

Johnson & Johnson Vision Care, Inc.

Endpoint Type	Endpoint	Two-sided Type I Error	Sample Size (N/arm)	Power
	Comfort throughout the day	0.025	118	80.2%
			153	90.1%
	Comfortable vision while night driving	0.0125	118	80.3%
			165	90.2%
			129	80.2%

As shown in Table 10, about 165 subjects per arm will be required to achieve a statistical power of 90% for all primary and secondary endpoints, assuming a 20% difference in the proportion of subjects endorsing T2B between the Test group and the Control group. Therefore, the plan is to enroll approximately 360 subjects with a target of 330 to complete the study (165 per arm).

14.3. Analysis Populations

Safety Population:

All subjects who are administered any test article excluding subjects who drop out prior to administering any test article. At least one observation should be recorded.

Per-Protocol Population:

All subjects who successfully complete all visits and do not substantially deviate from the protocol as determined by the trial cohort review committee prior to database hard lock. Justification for the exclusion of subjects with protocol deviations from the per-protocol population set will be documented in a memo to file.

Intent-to-Treat (ITT) Population:

All randomized subjects regardless of actual treatment and subsequent withdrawal from the study or deviation from the protocol. At least one observation should be recorded.

14.4. Level of Statistical Significance

The study-wise type I error rate will be controlled at two-sided 0.05 level using a multi-branched gatekeeping testing approach combined with the truncated Hochberg procedure. The primary endpoint (end of day comfort) will be tested at the two-sided type I error rate of 0.05. The primary endpoint will serve as a gatekeeper for the first two secondary endpoints (digital device use and comfort throughout the day), and the two secondary endpoints will gatekeep the last secondary endpoint.

If the primary hypothesis is met, the first two secondary endpoints will be tested using the truncated Hochberg procedure (Dmitrienko et al., 2008; Dmitrienko et al., 2011).^{10,11} A truncated version of the Hochberg procedure with a prespecified truncation fraction ($0 \leq f < 1$), which is separable, needs to be used within the family of the first two secondary endpoints for a positive alpha to be carried over to the last secondary endpoint if at least one null

Clinical Study Protocol

Johnson & Johnson Vision Care, Inc.

hypothesis is rejected. According to the truncated Hochberg procedure with a truncation fraction of $f = \frac{1}{2}$, the larger p-value obtained from these two secondary tests will be compared to the endpoint-specific alpha level 0.0375, and the smaller p-value will be compared to the endpoint-specific alpha level 0.025.

- If the secondary test with the larger p-value is successful and the one with the smaller p-value is not successful, then alpha of 0.025 passes to the last secondary endpoint (comfortable vision while night driving).
- If the secondary test with the smaller p-value is successful and the one with the larger p-value is not successful, then alpha of 0.0125 passes to the last secondary endpoint.
- If both secondary tests are successful, the unused alpha available for testing the last secondary endpoint will be 0.05.
- If both secondary endpoints fail to show superiority, the last secondary endpoint cannot be tested.

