14.6. Secondary Analyses

Secondary analyses will be conducted on the Intent-to-Treat (ITT) population with observed cases (use only available datapoints and no imputation for missing data).

Clinical Study Protocol

Johnson & Johnson Vision Care, Inc.

All secondary endpoints will be analyzed separately using the same model as described for the primary endpoint. Item responses will be converted into binary variables as follows: Excellent or Very Good = 1 and others = 0 for digital device use (“Reduction in the feeling of tired eyes from using a computer or other digital device”) and comfortable vision while night driving (“Ability to see comfortably while driving at night”), and Strongly Agree or Agree = 1 and others = 0 for comfort throughout the day (“I could wear these contact lenses comfortably for as long as I wanted to”).

According to the testing strategy presented in section 14, if the primary hypothesis is met, the secondary endpoints will be tested as follows:

- for the first two secondary endpoints (digital device use and comfort throughout the day), comparisons between Test and Control will be carried out using the corresponding adjusted two-sided CI (96.25% CI for alpha = 0.0375 or 97.5% CI for alpha = 0.025), depending on the relative magnitude of the obtained nominal p-values, constructed for the odds ratio (Test over Control) separately for each endpoint;
- for the last secondary endpoint (comfortable vision while night driving), a two-sided 95% CI (alpha = 0.05), 97.5% CI (alpha = 0.025), or 98.75% CI (alpha = 0.0125) will be estimated for odds ratio and the confidence level will be determined based on the success of the previously tested secondary endpoints.

Superiority will be declared if the lower bound of the corresponding CI is above 1.

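### The testing rule for the first two secondary endpoints contradicts the truncated Hochberg procedure it names: the larger p-value can succeed while the smaller fails, and 0.025 then passes to night driving

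*Combined protocol and SAP*

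**What the plan says.** Section 14.4 sets the overall aim: "The study-wise type I error rate will be controlled at two-sided 0.05 level using a multi-branched gatekeeping testing approach". If the primary hypothesis is met, "the first two secondary endpoints will be tested using the truncated Hochberg procedure", with a truncation fraction of one half. Under that procedure "the larger p-value obtained from these two secondary tests will be compared to the endpoint-specific alpha level 0.0375", and the smaller p-value is compared with 0.025.

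Four bullets then fix what night driving receives:

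- The first bullet begins "If the secondary test with the larger p-value is successful and the one with the smaller p-value is not successful" and passes 0.025.
- If only the smaller p-value succeeds, "then alpha of 0.0125 passes to the last secondary endpoint".
- If both succeed, 0.05 is available.
- If both fail, night driving is not tested.

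Section 14.6 carries the same logic into confidence intervals. Each of the two endpoints gets its own interval, 96.25% or 97.5%, "depending on the relative magnitude of the obtained nominal p-values", and is judged on that interval alone. For night driving, besides a 95% interval, a "97.5% CI (alpha = 0.025), or 98.75% CI (alpha = 0.0125) will be estimated for odds ratio". Neither section says that success of the larger p-value rejects both nulls.

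**The concern.** Hochberg's procedure and its truncated form step up from the larger p-value. If the larger p-value meets its cut-off, every null in the pair is rejected, because the other p-value is smaller still. An outcome in which the larger p-value succeeds and the smaller fails therefore cannot occur. Section 14.4 gives that outcome its own bullet and its own carry-over. Section 14.6 makes it reachable by judging each endpoint separately against a level set by rank.

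The synopsis describes this as a claims trial, so these are confirmatory decisions. If the data fell in the affected region, the written rule and the named method would support different claims, and someone would have to choose between them with the results in view.

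**Working it through.** **Inputs (section 14.4).** Alpha 0.05 two-sided, m = 2 endpoints, f = 1/2.

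**Cut-offs.** These reproduce:

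- Larger p: [f + (1 − f)/2] × 0.05 = 0.75 × 0.05 = 0.0375.
- Smaller p: [f/2 + (1 − f)/2] × 0.05 = 0.50 × 0.05 = 0.025.

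**Carry-over.** With k nulls retained, the pair uses [f + (1 − f)k/2] × 0.05 for k > 0 and nothing for k = 0. The remainder passes on:

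- k = 0: 0.05 (third bullet, correct).
- k = 1: 0.05 − 0.75 × 0.05 = 0.05 − 0.0375 = 0.0125 (second bullet, correct).
- k = 2: 0.05 − 0.05 = 0 (fourth bullet, correct).

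No value of k gives 0.025.

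**The rules side by side, both effects favouring Test:**

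| Larger p | Smaller p | As written | Truncated Hochberg |
|---|---|---|---|
| ≤ 0.0375 | ≤ 0.025 | both; 0.05 | both; 0.05 |
| > 0.0375 | ≤ 0.025 | smaller only; 0.0125 | smaller only; 0.0125 |
| ≤ 0.0375 | > 0.025 | larger only; 0.025 | both; 0.05 |
| > 0.0375 | > 0.025 | neither; stop | neither; stop |

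Only the third row differs. It is the region where both p-values lie in (0.025, 0.0375]. With p = 0.030 and 0.035, the plan declares superiority at 0.035, denies it at 0.030 and tests night driving at 0.025. The named procedure declares both and tests night driving at 0.05.

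**How often.** Normal approximation, 8 million draws per scenario, starting from 165 per arm. Control rates are 48, 41, 43 and 53% (section 14.2). Not Applicable shares from Table 9 are removed: device use 4.8% Test and 2.8% Control, night driving 2.2% and 2.8%. Effects are 20, 16, 13 and 10 points. The documents give no correlation between endpoints, so 0, 0.3, 0.5 and 0.8 are assumed.

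- Region together with primary success: 0.040–0.152% of trials at 20 points, 0.16–0.45% at 10–16 points.
- Simulation of the binary responses, 40,000 trials per scenario: 0.055–0.172% and 0.22–0.49%.
- Without requiring primary success: 0.04–0.20% and 0.2–0.7%.
- Within the region, the night-driving p-value falls in (0.025, 0.05], where the carry-over changes the result, in about 2–16% of cases at 20 points and 8–21% at 10–16 points. That is about 0.001–0.024% and 0.015–0.09% of all trials.

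**Power.** Pearson chi-square power for night driving at 73% vs 53% with 165 per arm is 90.2% at alpha 0.0125 (matching Table 10), 94.0% at 0.025 and 96.7% at 0.05.

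**Type I error.** When both effects favour Test, the written rule rejects a subset of what step-up rejects, so it cannot inflate error. One other route leads to the first bullet: ranking is by two-sided p-values, so the smaller one may favour Control. The written rule is then slightly more lenient. For two independent true nulls, in one-sided terms:

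- Step-up: 1 − 0.9875² + 0.00625² = 0.02488.
- As written: add 0.01875² − 0.0125² = 0.000195, giving 0.02508.

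The reference is 0.025. This wrong-direction route was not seen at 20 points and has probability of at most about 0.001% at 10–16 points. Simulated familywise error over the two endpoints and night driving stayed at 0.025 within simulation error in every configuration tried.

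**The case against.** Four points can be made for the plan.

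First, naming and citing a method without writing out its steps is not an error, and section 14.1 defers detail to a stand-alone SAP. That would answer a bare omission. It does not answer a bullet and an interval rule that contradict the method, and section 14.10 says the analysis follows the protocol's own sections.

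Second, 0.025 is not arbitrary. It is 0.05 minus the level of the failed test (0.05 − 0.025), the same subtraction that yields 0.0125 in the second bullet (0.05 − 0.0375). The accounting is consistent, but it is applied to a branch the procedure does not have. Under the procedure the carry-over depends on how many nulls are retained, not on which one.

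Third, the event is rare and, in the main region, conservative. This stands, and it limits the point to a wording correction.

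Fourth, ordering by one-sided p-values may look like a preference, since the wrong-direction case is negligible, and a one-sided 0.0125 beside a two-sided 0.0125 could confuse. The labelling risk is real, so each level needs its sidedness stated. The ordering itself is needed: under two-sided ranking, a stepwise rule would deny an endpoint favouring Test whenever the other endpoint had a smaller p-value favouring Control.

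**Conclusion.** The concern holds. The cut-offs of 0.0375 and 0.025 and the carry-overs of 0.0125 and 0.05 are correct. The first bullet of section 14.4, the separate rank-based intervals in 14.6 and the 97.5% interval for night driving do not belong to truncated Hochberg.

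The practical impact is low. The affected region with primary success arises in well under 1% of trials, and the night-driving result changes in less than 0.1%. These frequencies rest on the planned Control rates, equal effects across endpoints and assumed correlations of 0 to 0.8. The contradiction itself rests on none of them. Type I error is essentially unchanged; the excess of 0.02508 over 0.025 comes only from the wrong-direction route. The text should still be corrected, because a confirmatory decision rule is wrong as written.

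**What to change.** In section 14.4, delete the first bullet and state the rule in full:

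- Order the two endpoints by one-sided p-value for superiority of Test. The one-sided cut-offs are 0.01875 (larger) and 0.0125 (smaller), equal to two-sided 0.0375 and 0.025.
- If the larger p-value meets its cut-off, reject both nulls and pass two-sided 0.05 to night driving.
- Otherwise, if the smaller p-value meets its cut-off, reject that null only and pass two-sided 0.0125.
- Otherwise, do not test night driving.

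In section 14.6, replace the rank-based intervals with two steps, using the same ordering:

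- Step 1: construct the 96.25% interval for both endpoints. If both lower bounds exceed 1, both are superior.
- Step 2: otherwise the endpoint with the larger one-sided p-value is not superior, and the other is superior only if the lower bound of its 97.5% interval exceeds 1.

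Remove the 97.5% option for night driving, leaving 95% or 98.75%. Carry the same rule into the stand-alone SAP.

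The cost is a wording change. Table 10 used 0.05, 0.025 and 0.0125, which remain valid, so no subjects are added.
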